8.3.3.2 PD-1/PD-L1 expression and response

For each dose level as well as for each individual expansion cohort, Fisher's exact test will be used to test the association of baseline tumor and T-cell PD-L1/PD-1 immunohistochemical expression with disease response.

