1.8 Rationale for the Study Design

This study will evaluate the pathologic and immunologic changes induced by atezolizumab-based therapy in bladder tissues compared to pretreatment biopsies. This study has two cohorts (Cohort A and Cohort B) and will accrue each cohort sequentially (i.e., Cohort A will fully accrue, then Cohort B).

Cohort A: Atezolizumab Monotherapy

In the initial monotherapy multi-dose phase (Cohort A), the effects of increasing numbers of doses of atezolizumab will be explored. Similarly, the safety, feasibility, and efficacy of administering up to 3 doses of atezolizumab in patients scheduled for cystectomy will also be examined.

- Multi-dose phase (fully accrued as of October 2020): A fixed number of 6 patients will be accrued at each dose level in the multi-dose portion of the study to allow for investigation into the immunologic impact of different cumulative doses of atezolizumab prior to cystectomy. It is unknown whether multiple doses of atezolizumab are necessary to achieve a complete response or a durable remission as opposed to a single dose, and accrual of 6 patients at each dose level will allow for a preliminary estimate of the efficacy of each cumulative dose level. The safety profile of atezolizumab is well established from multiple Phase I - III studies, and treatment related Grade 3 or 4 toxicities were rare. The multi- dose portion may better inform future studies of neoadjuvant atezolizumab and potentially allow for shorter neoadjuvant courses to be administered.

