- Cohort A expansion phase opened after the multi-dose portion of Cohort A completed, consisting of up to 27 total patients in Cohort A. In order to reduce the number of subjects needed for this study and allow for faster study completion, the 6 subjects treated at the highest dose from the multi-dose phase of the study will be included as part of the expansion cohorts, therefore the total accrual to the expansion cohort after the multi-dose portion of Cohort A will be up to 9 subjects. The highest dose level is chosen for the expansion cohorts as it is expected that administration of multiple doses of atezolizumab will best enhance immune responses and lead to better clinical responses. These expansion cohorts will allow for a better estimate that treatment-related grade 3 or 4 events, or delays in cystectomy >12 weeks, are observed at a frequency of less than <33%. It will also allow for an exploratory estimation of efficacy of atezolizumab in this setting, and for further characterization of the immunologic effects of atezolizumab in this patient population.

Cohort B: Atezolizumab + Tiragolumab

After completion of enrollment into Cohort A, and upon approval of Amendment 4.3 (October 19, 2020) the study will begin accrual into Cohort B, where participants will receive combination neoadjuvant therapy with atezolizumab (1200mg IV on Day 1 of a 21 day cycle) and tiragolumab (600mg IV on Day 1 of a 21 day cycle) as neoadjuvant treatment for an intended total of three treatment cycles prior to an intended radical cystectomy. Similar to Cohort A, the safety and efficacy of administering up to 3 doses of atezolizumab in combination with tiragolumab preoperatively in patients scheduled for cystectomy will be examined. No adjuvant therapy will be offered as no study to date has shown benefit for adjuvant PD-1 therapy in urothelial cancer patients who had received prior immunotherapy.²⁸ Recently Checkmate-274 study had a press release indicating a DFS benefit for nivolumab over placebo for high-risk patients with urothelial cancer following radical cystectomy however none of these patients have had prior neoadjuvant immunotherapy.

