3.2 Number of Participants

Total Cohort A accrual: Up to 27 participants

- Cohort A Safety Lead-In: 18 participants (already accrued as of October 2020)
- Cohort A Expansion: Up to 9 additional participants may be accrued so that Cohort A expansion group = up to 15 total participants treated at established regimen (6 participants treated at highest administered dose from multi-dose portion + up to 9 additional participants).

Total Cohort B accrual: 21-33 patients

- Cohort B Safety Lead-In: 6-18 patients will be included.
- Cohort B Expansion: 15 additional patients treated with the regimen established during the safety lead-in phase (21 total treated with established regimen)

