8.3.4.1 Tumor PD-L1 assessment

PD-L1 protein expression on tumor tissue from pre-treatment biopsies, cystectomy specimens, and any other tumor biospecimens obtained will be evaluated immunohistochemically and scored on a scale of 0, 1, 2, or 3. This scoring will be used for the determination of relationships between tumor PD-L1 expression and clinical responses described above.

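### The PD-L1/PD-1 versus response test is run only within separate strata, some of 6 patients, where a two-sided 2x2 Fisher p-value cannot fall below 0.067; no combined analysis is planned

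*Combined protocol and SAP*

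**What the plan says.** Section 8.3.3.2 is the analysis text for the association of baseline PD-L1/PD-1 expression with response. Fisher's exact test is to be run "For each dose level as well as for each individual expansion cohort". It gives no significance level, sidedness, expression cut-point or response categories, and no pooled or stratified test.

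The group sizes come from elsewhere:

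- **Cohort A dose levels (section 1.8):** "A fixed number of 6 patients will be accrued at each dose level in the multi-dose portion of the study". There are three levels, so 18 patients.
- **Cohort A expansion (sections 1.8 and 3.2):** it takes in "the 6 subjects treated at the highest dose from the multi-dose phase" plus up to 9 more, so up to 15.
- **Cohort B (section 3.2):** "Cohort B Safety Lead-In: 6-18 patients will be included", in groups of 6 per level tried (section 3.1), then "21 total treated with established regimen".

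Section 8.3.4.1 says PD-L1 is "scored on a scale of 0, 1, 2, or 3". Section 2.2 lists the association as item 4 of the secondary endpoints for the expansion cohorts.

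**The concern.** An exact test on 6 patients has very few possible outcomes, and its p-value has a floor set by the sample size. If that floor lies above the significance level, the test is non-significant whatever the data show. If it lies just below, only the most extreme table counts.

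The second issue is wider than the 6-patient groups. Every test is confined to one stratum, so information that is consistent across strata is never added up. In Cohort A, the 12 patients at dose levels 1 and 2 belong to no expansion group. For this endpoint their data appear only in the 6-patient tests. Fisher's test also ignores the ordering of the 0-3 score.

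**Working it through.** **1. The plan's own figure.** No power is stated for this test. The nearest figure is in section 8.1: 6 per cohort gives 80% power for effect size 1.5 at level 0.1, for the T-cell endpoint. Taking 0.1 as two-sided, n per group = 2(1.645 + 0.842)²/1.5² = 2 × 6.185/2.25 = 5.5, rounded up to 6. So the group size of 6 reproduces, but it was chosen for a continuous endpoint.

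**2. Floor with 6 patients, yes/no response.** For a perfectly separated table with k patients in one group, the conditional probability is 1/C(6,k).

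| Split | Smallest two-sided p |
|---|---|
| 1 vs 5 | 1/6 = 0.167 |
| 2 vs 4 | 1/15 = 0.067 |
| 3 vs 3 | 2/20 = 0.10 |

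Unequal margins (for example 2 high expressors and 3 responders) give larger values. The one-sided minimum is 1/20 = 0.0500, which is not below 0.05. Keeping three or four expression levels against a yes/no response does not help: the minima are 0.067 and 0.10. With n=15 and n=21 the 2x2 minima are 0.00016 and 0.000003, so there is no practical floor.

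**3. Power with 6 patients at 0.1.** Inputs are from the pembrolizumab trial described in section 1.5: 35 of 50 patients PD-L1 high (0.70), pT0 0.543 if high and 0.133 if low. Only perfectly separated 2/4 splits give p < 0.1:

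- 4 high, all respond; 2 low, none respond: 15 × 0.7⁴ × 0.3² × 0.543⁴ × 0.867² = 0.0212
- 2 high, both respond; 4 low, none respond: 15 × 0.7² × 0.3⁴ × 0.543² × 0.867⁴ = 0.0099
- the same splits with the association reversed: about 0.0003

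The total is about 0.031. If p exactly 0.10 also counts, perfect 3/3 splits raise it to 0.051.

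**4. Power at two-sided 0.05, same inputs.** Full enumeration of the binomial outcomes for a single Fisher test gives 0% at n=6, 17% at n=15 and 29% at n=21.

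**5. Power of a stratified exact test.** The statistic is the number of PD-L1-high responders summed over strata. Its null distribution is the convolution of the strata's hypergeometric distributions, and the two-sided p adds all outcomes no more probable than the one observed. Simulated power at 0.05 under the same inputs:

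| Strata | Patients | Power |
|---|---|---|
| Cohort A: 6, 6, 15 | 27 | about 37% |
| Both cohorts: 6, 6, 15, 21 | 48 | about 71% |

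The six Cohort A level-3 patients are counted once, inside the 15. Simple unstratified pooling would give 42% and 74%. The stratified figures are the ones that apply to the recommendation.

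**The case against.** Four objections carry weight.

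- **Significance level.** The plan sets none for this test, so 0.05 is the reader's assumption. The only level attached to the 6-patient Cohort A groups is 0.1, and there a perfectly separated 2/4 split is significant. A reader might infer that the dose-level tests can never be positive; the documents do not support that. What stands is no chance at two-sided 0.05 with yes/no response and about 3% at 0.1.
- **Response categories.** Section 7.1.1 defines both complete and near-complete pathologic response. A three-by-three table with 6 patients could reach 1/60 = 0.017. Section 8.3.4.3 contrasts responders with non-responders, so yes/no is the likelier reading, but section 8.3.3.2 does not say so.
- **Scope.** The secondary endpoint is listed for the expansion cohorts, whose tests have no floor. A reader might infer that the endpoint as a whole cannot be answered; that goes too far. The expansion tests are weak under the stated assumption, not empty.
- **Consequences.** Nothing in the plan says a non-significant dose-level result will be reported as absence of association, and no stopping rule or sample size depends on this test. The misreading is a risk, not something planned.

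There is also a reason to look at levels separately: Cohort A's multi-dose phase was designed to compare cumulative doses, and Cohort B adds a second drug. That supports showing per-level data. It does not support making a test on 6 patients the inference.

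**Conclusion.** The point holds as a weakness of analysis choice. With yes/no response, the 6-patient Fisher tests cannot reach two-sided 0.05 and have about 3% power at 0.1. The expansion tests have about 17% and 29% power at 0.05, the first assuming the full 15 are accrued. Combining strata raises the best available power from 29% to about 71%, and roughly doubles it within Cohort A (17% to 37%), with no added patients.

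The floor is exact arithmetic. The power figures are conditional: they borrow an association from a trial of a different drug with a different assay and cut-point, and only 15 patients in its low-expression group. They show relative gains better than absolute power. Even after the change, Cohort A alone stays below 50%. Cohort B alone stays near 29%, unless further lead-in levels are opened and included as strata.

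**What to change.** Reword section 8.3.3.2 as follows:

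1. Make the inferential analysis an exact test stratified by dose level and cohort: exact Cochran-Mantel-Haenszel on a stated cut-point, or an exact stratified trend test on the 0-3 score. Run it within Cohort A and, as a further analysis, across both cohorts. Count each patient in one stratum only. The power figures above are for the cut-point version; the trend version was not evaluated.
2. Report the 6-patient dose levels descriptively, as tables of expression against response without p-values.
3. State the significance level, sidedness, expression cut-point (if used) and response definition for this test.
4. Show per-cohort results beside the combined result.

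The cost is SAP wording only; no extra patients or samples are needed. The statistical cost is an assumption of a broadly common association across dose levels and, for the combined test, across monotherapy and combination. Step 4 lets the reader judge that.

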8.3.4 Analysis of Exploratory Endpoints: Tissue based endpoints

Note: Tissue will be used for multiple different exploratory assays. In the event that there is insufficient tissue to perform all assays for an individual subject, the tissue should be prioritized

for assays as follows, in which the first assay described is the highest priority. Also note that PD-L1 immunohistochemistry and immune cell mRNA signature assays will be performed at Genentech, while all other assays will be performed at UCSF.

8.3.4.1 Tumor PD-L1 assessment

PD-L1 protein expression on tumor tissue from pre-treatment biopsies, cystectomy specimens, and any other tumor biospecimens obtained will be evaluated immunohistochemically and scored on a scale of 0, 1, 2, or 3. This scoring will be used for the determination of relationships between tumor PD-L1 expression and clinical responses described above.

8.3.4.2 Tissue immune subset quantification and localization

For all subjects, immune cell subsets and localization will be summarized by changes from baseline to after treatment using descriptive statistics.

8.3.4.3 Immune cell mRNA signatures of response

To identify individual genes whose expression levels at pre-treatment are associated with pCR, we will apply two-sample *t* tests to compare responders and non-responders. Adjusted P values controlling for false discovery rate (Benjamini and Hochberg method) will be derived. In addition, to assess association of pre-specified immune gene signature with response, the median expression level of the component genes will be used to represent the signature and two-sample *t* tests will be used. For genes or signatures that emerge as significantly associated with response, logistic regression models will be used to assess their independent association with response after adjusting for known clinical prognostic factors. To identify pharmacodynamic markers, paired *t*-test will be carried out to examine immune gene expression differences between pre-treatment and at-cystectomy samples. Additionally, association of gene expression levels at time of cystectomy with long term efficacy outcomes, such as PFS and DFS, will be explored using the Cox proportional hazards regression model. Hierarchical clustering superimposed with response status, relevant baseline or prognostic characteristics or experimental factors will be performed using Spearman correlation and complete linkage to visualize the discriminating power of the immune gene expression and the correlative structure among the genes and the samples.

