2.3 Exploratory (Correlative) Objectives

1. To define the immunologic infiltration within bladder tissue following administration of neoadjuvant combination treatment with atezolizumab and tiragolumab when compared to pre-treatment TURBT biopsies
2. To assess the immunologic impact of combined tiragolumab and atezolizumab regimen in the urothelial cancer tumor microenvironment (Cohort B) in comparison to the impact on the tumor microenvironment of atezolizumab monotherapy in a similar cohort of patients treated with neoadjuvant atezolizumab for MIBC at UCSF (Cohort A)
3. To assess for tumor-based biomarkers of response and resistance to this combination therapy using single-cell RNA sequencing (scRNA-seq) and high-dimensional flow cytometry
4. To define the treatment-induced effects on circulating immune cells with this combination therapy
5. To assess the presence of antigen-specific immune responses to a broad panel of candidate tumor antigens

Endpoints:

- Immunohistochemistry and gene expression analysis for immune cell subset quantification and localization within resected tumors, in particular through the comparison of intratumoral environment of post-treatment cystectomies to pre-treatment TURBTs
- Flow cytometry to evaluate changes in intratumoral and circulating immune cells
- T cell receptor (TCR) deep sequencing of tissue samples from pre-treatment biopsies and post-treatment resected tissues, and post-cystectomy circulating T cells.
- Immune response mRNA expression analysis to derive signatures associated with tumor response
- Identification of genomic mutations and gene copy aberrations associated with response and resistance to therapy
- Antigen array-base detection of circulating antibody responses
- Flow cytometry to evaluate changes in intratumoral and circulating immune cells
- T cell receptor (TCR) deep sequencing of tissue samples from pre-treatment biopsies and post-treatment resected tissues, and post-cystectomy circulating T cells.
- Immune response mRNA expression analysis to derive signatures associated with tumor response (expansion only)

- Identification of genomic mutations and gene copy aberrations associated with response and resistance to therapy (expansion only)
- Antigen array-base detection of circulating antibody responses (expansion only)

3 Study Design

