8.1 Determination of Sample Size and Power Calculation

Cohort A

Multi-dose phase: With 6 patients in each cohort, there will be 80% of power to detect the effect size of 1.5 at significance level of 0.1. For the lowest dose level, a 2-fold increase from pre-treatment to post- treatment is expected, if at the higher dose level, there is more than 3-fold increase, assuming the standard deviation equals 1, then there will be 80% power to detect significant treatment effect on the intratumoral immune response.

Expansion phase: Data from a study of intravesical valrubicin chemotherapy in BCG refractory patients³⁴ demonstrated that a 21% CR rate is achievable at 6 months. Assuming a 5% (null) CR rate for untreated patients at 6 months, 15 patients would be required to observe an improvement to a 36% CR rate at 6 months in response to-PD-L1 therapy (effect size = 0.642), at a significance level of 0.1 with 80% power.

Cohort B

A pT0 rate at cystectomy was observed for ~30% of patients treated with immune checkpoint inhibitors monotherapy based on published Phase II clinical trials. In order to observe an improvement from a 30% CR rate (null hypothesis) to 60% CR rate (alternative hypothesis) with the combination of atezolizumab and tiragolumab a total of 21 patients are required in Cohort B assuming a significance level of 0.05 and 80% power.

Using these assumptions, following a lead in safety phase of 6 patients at a combination regimen that is deemed to be safe based on the criteria outlined above, a further 15 patients will be enrolled at the same regimen. This will make a total of 21 patients to be treated in Cohort B with the intended regimen.

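### The adjusted logistic models for response genes and signatures carry a substantial risk of separation if fitted by standard maximum likelihood within one expansion cohort; Firth-penalised fitting would avoid it.

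*Combined protocol and SAP*

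**What the plan says.** Section 8.3.4.3 takes two kinds of predictor forward.

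- Single genes are compared between responders and non-responders by t test, and "Adjusted P values controlling for false discovery rate (Benjamini and Hochberg method) will be derived".
- A further t test is used to "assess association of pre-specified immune gene signature with response".

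For whatever is significant, "logistic regression models will be used to assess their independent association with response after adjusting for known clinical prognostic factors". The section does not name or count those factors. It also does not give the false discovery level, the number of genes, the fitting method, the test, or what to do if a fit does not converge. It does not say whether the two cohorts are analysed separately.

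On sample size, Section 3.2 gives "Cohort A expansion group = up to 15 total participants treated at established regimen" and, for Cohort B, "21 total treated with established regimen". Section 2.3 lists the mRNA response-signature endpoint twice, once limited to expansion patients and once without that limit. Section 8.3.4 ranks the tissue assays by order of description for cases of scarce tissue. The mRNA assay is third, so fewer patients than these may have data.

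**The concern.** Unqualified logistic regression is normally read as maximum likelihood. In a small sample, a predictor already chosen because it divides responders from non-responders may, together with a few covariates, classify every patient correctly. The maximum-likelihood coefficient is then infinite (separation), and software returns a non-convergence warning or an arbitrary large odds ratio with a huge standard error. When the estimate is finite but close to separation, it is inflated and the Wald test loses power.

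This model is the only step in Section 8.3.4.3 that formally adjusts a response association for clinical prognosis. A marker that truly predicts response could be reported with a meaningless odds ratio, or called not independent, because of the estimator rather than the biology.

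**Working it through.** **1. Sample sizes.** Section 8.1 states that "a total of 21 patients are required in Cohort B assuming a significance level of 0.05 and 80% power", for 30% against 60%. With the arcsine effect size h = 2·asin√0.60 − 2·asin√0.30 = 1.772 − 1.159 = 0.613, n = ((1.960 + 0.842)/0.613)² = 20.9, so 21. For the Cohort A expansion, Section 8.1 gives effect size 0.642, significance level 0.1 and 80% power. Taken as two-sided, n = ((1.645 + 0.842)/0.642)² = 15.0. Both stated figures are reproduced.

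**2. Smaller outcome group at the Section 8.1 rates.**
- Cohort A at 36%: 15 × 0.36 = 5.4.
- Cohort B at 30%: 21 × 0.30 = 6.3.
- Cohort B at 60%: 21 × 0.40 = 8.4.

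That is about 5 to 8 patients.

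**3. Assumptions the plan does not supply.**
- Expression is normal with SD 1, shifted by d in responders. The true logistic slope is then d per SD.
- Covariates are unrelated to response, so the marker really is independent of them.
- The strict screen is p < 0.0002, the Benjamini-Hochberg cut-off when one gene of 500 passes at a 10% false discovery rate (0.10/500). If R genes pass, the cut-off is R × 0.0002; 50 genes give 0.01.
- A signature enters at p < 0.05.

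**4. Separation rates.** Separation was detected by linear programming in 250 to 300 selected data sets per cell. Monte Carlo standard error is at most √(0.25/250) = 3.2 percentage points. "Binary" covariates are 50/50. "Mixed" covariates alternate binary (about 40% prevalence) and continuous. Response is about 30-36% at n=15, 30% or 60% at n=21, and 40% at n=36. Entries are one factor / three factors unless marked.

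| Predictor and screen | d | Covariates | n=15 | n=21 | n=36 |
|---|---|---|---|---|---|
| Gene, p<0.0001 | 1.5 | mixed | 91-92% / 99% | 28-45% / 73-78% | not run |
| Gene, p<0.0002 | 1.5 | binary | 86-96% (1 to 3) | 27-69% (1 to 3) | not run |
| Gene, p<0.001 | 1.5 | mixed | 65-73% / 94-95% | 17-19% / 48-59% | 1% / 3% |
| Gene, p<0.01 | 1.5 | binary | not run | 8-17% / 36-38% | not run |
| Signature, p<0.05 | 1.2 | mixed | 25% / 61% | 3-7% / 20-26% | 0% / 1% |

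With binary covariates, signatures and loosely screened genes together gave about 6-43% at n=21 with one to three factors. Repeats of the p<0.0002 case put the lower end at n=21 between 24% and 27%.

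**5. Quality of the fits.**
- Coefficients (p<0.0002, true slope 1.5): the median finite maximum-likelihood estimate was 3.9 to 5.2. Firth fits were finite in every run, with medians of 1.5 to 2.3.
- Wald p<0.05 (p<0.0002 screen): 0-1.3% of runs at n=15 and 7-37% at n=21. For a 1.2 SD signature it was 2-6% and 30-67%.
- Precision (signature, finite fits): the ratio of upper to lower 95% limit for the odds ratio was about 36- to 42-fold at n=21 with 30% response and one factor. With three factors it was 57- to 86-fold at n=21, about 710- to 780-fold at n=15, and about 9- to 14-fold at n=36.

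**The case against.** Several points on the other side stand.

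- **Pooling.** Sections 8.3.3.2, 8.3.4.4, 8.3.4.5 and 8.3.5.1 specify analysis by dose level or cohort; Section 8.3.4.3 does not. Pooling the expansion groups (15 + 21 = 36) makes separation rare, although it mixes monotherapy with combination treatment.
- **Test.** The plan names no test. Under the p<0.0002 screen, a likelihood-ratio test from the same model gave p<0.05 in every run, including at n=15. That test is anticonservative at these sizes, so this does not validate the analysis. It does mean that loss of power is a feature of the Wald test, not of everything the text permits.
- **Screen.** Benjamini-Hochberg is a step-up procedure, so p<0.0002 is a harsh case. Signatures face only an ordinary t test.
- **Inflation.** Part of the excess in the coefficients is selection bias, which no change of estimator removes. The Firth medians sit close to the true value partly because shrinkage and selection pull in opposite directions.
- **Status.** The endpoint is exploratory. The same section also overlays prognostic characteristics on the clustering, so prognosis is examined descriptively as well.

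A reader might infer that the model will usually fail in 15 to 21 patients and cannot give a usable estimate. The documents do not support that. Neither the number of factors nor the fitting method is stated. At n=21, most fits in these simulations do not separate for signatures with one to three factors, or for genes with one factor.

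**Conclusion.** The point holds as a conditional one. Under maximum likelihood within a single expansion cohort, separation is likely at n=15 for stringently selected genes (about 86-96%). At n=21 it ranges from a material risk to more likely than not for such genes (about 27-69%), and it is about 6-43% for signatures or looser screens. Finite odds ratios are inflated and have very wide limits. These rates rest on assumed differences of 1.2 to 1.5 SD, one to three binary covariates unrelated to response, and assumed screening thresholds; none of these is in the plan. The consequence is confined to an exploratory biomarker analysis. This is a worthwhile low-cost improvement and does not threaten the trial's primary conclusions.

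**What to change.** In Section 8.3.4.3, replace the unqualified logistic regression with Firth-penalised logistic regression, using profile penalised-likelihood confidence intervals and tests. Report the result as an adjusted estimate from the same data used to select the gene or signature, not as evidence of independence. Naming the clinical factors and stating whether the cohorts are pooled would make the model reproducible. Limiting each model to one factor is a trade-off for the study team and not a necessary part of the change.

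The cost is SAP wording and a standard software routine. The downside is that estimates are shrunk towards zero, and selection bias is reduced but not removed.
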